6.2 Nonserious Adverse Events

A *nonserious adverse event* is an AE not classified as serious.

6.2.1 Nonserious Adverse Event Collection and Reporting

The collection of nonserious AE information should begin at initiation of study drug. Nonserious AE information should also be collected from the start of a placebo lead-in period or other observational period intended to establish a baseline status for the subjects.

Nonserious AEs should be followed to resolution or stabilization, or reported as SAEs if they become serious (see Section 6.1.1). Follow-up is also required for nonserious AEs that cause interruption or discontinuation of study drug, or those that are present at the end of study treatment as appropriate. All identified nonserious AEs must be recorded and described on the nonserious AE page of the CRF (paper or electronic).

Completion of supplemental CRFs or questionnaires may be requested for AEs and/or laboratory abnormalities that are reported/identified during the course of the study.

See Section 6.7.1; regarding the collection and reporting of non-serious events necessary to meet the postmarketing commitments required by the FDA.

6.3 Laboratory Test Abnormalities

The following laboratory abnormalities should be captured on the nonserious AE CRF page or SAE Report Form as appropriate:

- Any laboratory test result that is clinically significant or meets the definition of an SAE
- Any laboratory abnormality that required the subject to have study drug discontinued or interrupted
- Any laboratory abnormality that required the subject to receive specific corrective therapy.
- Any microscopic hematuria with **NO** common cause identified, if a malignancy is otherwise suspected or positive hematuria (by microscopy) at the unscheduled repeat visit (See section 5.3.2.2 & appendix 3)

It is expected that, wherever possible, the clinical, rather than the laboratory term would be used by the reporting investigator (eg, anemia versus low hemoglobin value).

6.4 Pregnancy

If, following initiation of the investigational product, it is subsequently discovered that a study subject is pregnant or may have been pregnant at the time of investigational product exposure, including during at least 6 half lives after product administration, the investigational product will be permanently discontinued in an appropriate manner (eg, dose tapering if necessary for subject safety). Protocol-required procedures for study discontinuation and follow-up must be performed on the subject unless contraindicated by pregnancy (eg, x-ray studies). Other appropriate pregnancy follow-up procedures should be considered if indicated.

The investigator must immediately notify the BMS (or designee) Medical Monitor of this event and complete and forward a Pregnancy Surveillance Form to BMS (or designee) within 24 hours and in accordance with SAE reporting procedures described in Section 6.1.1.

Follow-up information regarding the course of the pregnancy, including perinatal and neonatal outcome and, where applicable, offspring information must be reported on the Pregnancy Surveillance Form.

Any pregnancy that occurs in a female partner of a male study participant should be reported to the sponsor. Information on this pregnancy will be collected on the Pregnancy Surveillance Form.

6.5 Overdose

An overdose is defined as the accidental or intentional administration of any dose of a product that is considered both excessive and medically important. All occurrences of overdose must be reported as an SAE (see Section 6.1.1 for reporting details.).

6.6 Potential Drug Induced Liver Injury (DILI)

Wherever possible, timely confirmation of initial liver-related laboratory abnormalities should occur prior to the reporting of a potential DILI event. All occurrences of potential DILIs, meeting the defined criteria, must be reported as SAEs (see Section 6.1.1 and Appendix 5 for more details).

6.7 Other Safety Considerations

Any significant worsening noted during interim or final physical examinations, electrocardiograms, x-rays, and any other potential safety assessments, whether or not these procedures are required by the protocol, should also be recorded as a nonserious or serious AE, as appropriate, and reported accordingly.

6.7.1 AE's of Special Interest

Event categories of special interest for this study may include, but are not limited to, skin, decreased lymphocyte count, decreased thrombocyte count, infection, opportunistic infection, pancreatitis, hepatic, fracture, hypersensitivity, worsening renal function, genital infections, urinary tract infections, bladder neoplasm, and breast neoplasm.

For the purposes of regulatory reporting, the following events must be reported in 24 hours regardless of whether the events are classified as serious or non-serious:

Liver test abnormalities accompanied by jaundice or hyperbilirubinemia

This category of events includes all AEs where hepatocellular damage (with elevation of ALT or AST > 3 times the upper limit of normal) is combined with hepatic dysfunction (with elevation of total bilirubin > 2.5 times upper limits of normal) or jaundice. With respect to LFT abnormalities, both central-lab results and adverse events will be monitored.

Opportunistic infections

This category of events includes infections of interest that are consistent with AIDS-defining diagnoses and are specific for immunosuppression, including unusual infections caused by bacteria, mycobacteria, fungi, viruses and protozoa. Herpes Zoster is of interest only if the case is multidermatomal, neurological or systemic.

Severe Hypersensitivity

This category of events includes all cases of severe hypersensitivity including: angioedema, anaphylaxis, and Stevens-Johnson Syndrome.

When one of these events meets the criteria for a serious adverse event, report the event using SAE reporting procedures (Section 6.1.1). When one of these events does not meet the criteria for a serious adverse event, report the event within 24 hours as a non-serious event.

For each non-serious event in these four categories, notify the Medical Monitor within 24 hours to discuss next steps in reporting.

7 DATA MONITORING COMMITTEE AND OTHER EXTERNAL COMMITTEES

7.1 Cardiovascular Adjudication Committee

An Independent Adjudication Committee, blinded to the treatment of the subjects, will classify cardiovascular adverse events, such as, but not limited to, death, myocardial infarction, and stroke reported in the study. A separate Adjudication Manual will define and describe the procedure for the handling, reporting and classification of these events.

Please also refer to Section 5.3.3.

7.2 Hepatic Adjudication Committee

An Independent Adjudication Committee, blinded to the treatment of the subjects, will determine the probability that drug-induced liver injury (DILI) is the cause of liver-related abnormalities, including but not limited to hepatic disorders leading to discontinuation from study treatment and/or death, liver laboratory abnormalities such as elevated AST and/or ALT with or without TB elevations (see Section 5.3.4 for more details).

A separate Adjudication Manual will define and describe the procedure for the handling, reporting and classification of these events.

8 STATISTICAL CONSIDERATIONS

8.1 Sample Size Determination

The mean change from baseline in HbA1c at Week 24 will be assessed comparing the saxagliptin 5 mg plus dapagliflozin 10 mg add-on to metformin treatment group versus each of the two monotherapy add-on treatment groups (dapagliflozin 10 mg plus placebo added to metformin and saxagliptin 5 mg plus placebo added to metformin). The min test approach of Laska and Meisner ⁵ will be implemented to test the simultaneous addition of saxagliptin and dapagliflozin to metformin versus each of the individual add-on components plus placebo. Statistical significance of the primary endpoint will be claimed if the p-values for both comparisons are significant at the 2-sided, 0.05 significance level.

Power calculations for longitudinal repeated measures analyses depend on many factors, including the pattern of drop out over time and correlations among the various time points included in the model. The choice of these parameters will affect any estimates of power, and their true values may not be known. Based on comparisons of results of longitudinal repeated measures analyses and analysis of covariance using last observation carried forward (ANCOVA with LOCF) from previous diabetes trials, the estimated standard errors of the treatment differences were similar between analyses. Therefore, power calculations are based on ANCOVA with LOCF, with the expectation that this will provide a good estimate of the power for the primary analysis using a longitudinal repeated measures model.

With 163 subjects per treatment group, there will be 90% power to detect a difference in mean HbA1c of 0.4% between the saxagliptin plus dapagliflozin mg added to metformin treatment group and each of the monotherapy add-on groups, assuming a standard deviation of 1.0%. Assuming that 5% of subjects do not have a post-baseline assessment, a total of approximately 516 subjects (172 subjects per treatment arm) need to be randomized.

Assuming that 50 % of screened subjects will fail to meet screening criteria, a total of 1032 subjects need to be screened.

8.2 **Populations for Analyses**

- The Enrolled Subjects Data Set will consist of all subjects who sign informed consent.
- The Randomized Subjects Data Set will consist of all randomized subjects who receive at least one dose of study medication during the double-blind treatment period. This is also known as the Intent to Treat (ITT) population. This will be the primary efficacy data set. Data in this data set will be analyzed based on randomized treatment group.
- The Evaluable Subjects Data Set will be a subset of the Randomized Subjects, with all data points collected after a relevant protocol deviation excluded from the data set. Relevant protocol deviations are defined as deviations that could potentially affect the interpretability of the study results. This is also known as the Per-protocol population. This data set will be used for sensitivity analyses of the primary efficacy endpoint if > 10% of subjects in any treatment group have relevant protocol deviations.
- The Treated Subjects Data Set will consist of all subjects who receive at least one dose of study medication during the double-blind treatment period. This will be the primary safety data set. Data in this data set will be analyzed based on randomized treatment, except in cases where a subject received a different treatment for the entire course of his/her participation in the double-blind treatment period. In this case, safety data for such a subject will be analyzed based on the first treatment the subject actually received.

8.3 Endpoint Definitions

8.3.1 Primary Efficacy Endpoint

• Mean change from baseline in HbA1c at Week 24

8.3.2 Secondary Efficacy Endpoints

- Mean change from baseline in 2-hour post-prandial glucose during a liquid meal test (2-h MTT) at Week 24
- Mean change from baseline in fasting plasma glucose (FPG) at Week 24
- Percent of subjects achieving a therapeutic glycaemic response, defined as a HbA1c < 7.0% at Week 24
- Mean change from baseline in body weight at Week 24 with the addition of saxagliptin and dapagliflozin to metformin vs. the addition of placebo and saxagliptin to metformin.

8.3.3 Exploratory Endpoints

- The percent of subjects who require glycemic rescue or discontinue study treatment for lack of efficacy up to Week 24.
- Time to glycemic rescue or discontinuation for lack of efficacy in the double-blind treatment period.
- Mean change from baseline in AUC glucose, AUC insulin, AUC C-peptide and AUC glucagon obtained during MTT at Week 24.
- Mean percent change from baseline in fasting serum lipids (Total-C, LDL-C, HDL-C, TG) during the double-blind treatment period.

8.4 Analyses

Analysis of data from the double-blind treatment period will be performed after all subjects have completed or discontinued from this period. In addition, all relevant queries must be answered and the database must be locked for the double-blind treatment period prior to the analysis.

8.4.1 Demographics and Baseline Characteristics

Demographic and baseline characteristics will be summarized using frequency distributions and descriptive statistics using the Randomized Subjects data set, for each treatment group as well as for all subjects combined. Key baseline characteristics that will be summarized include: age, gender, race, ethnicity, geographic region, body weight, body mass index (BMI), duration of type 2 diabetes, baseline HbA1c, baseline FPG, 2-hour post-prandial glucose during a liquid meal test, metformin formulation at

screening, and metformin daily dose. Baseline is defined as the last measurement prior to the first dose of double-blind study medication. No statistical tests will be performed to compare treatment groups at baseline. Additional analyses will be performed using available data.

8.4.2 Efficacy Analyses

All efficacy analyses will be performed using the Randomized Subjects data set. In addition, the primary efficacy analysis will be performed using the Evaluable Subjects data set if > 10% of subjects in any treatment group has relevant protocol deviations.

8.4.2.1 Primary Efficacy Analysis

The primary efficacy analysis will be performed using a longitudinal repeated measures analysis with terms for baseline value, treatment group, time, the interaction of treatment group and time, and the interaction of baseline value and time, including observations prior to rescue. Point estimates and 95% confidence intervals will be calculated for the adjusted mean changes within each treatment group as well as for the differences in adjusted mean changes between treatment groups.

Sensitivity analyses for HbA1c will include additional repeated measures analyses and analysis of covariance (ANCOVA) analyses. The repeated measures analyses will include two separate analyses including values after rescue, including and excluding a time-dependent covariate for rescue. Two separate ANCOVA analyses of the change from baseline at Week 24 will be performed, with terms for treatment group and baseline value in the model. One analysis will be based on measurements at Week 24 (if prior to rescue, if applicable) or the last post-baseline measurement prior to Week 24 and prior to rescue (if applicable), if no Week 24 assessment is available (ie. last observation carried forward [LOCF]). The second sensitivity analysis using ANCOVA will be based on all subjects completing the short-term double-blind period without requiring glycemic rescue therapy.

8.4.2.2 Secondary Efficacy Analyses

In order to protect the overall type I error rate, the interpretation of the statistical significance of treatment comparisons for each secondary efficacy endpoint will be done using a step-wise procedure. The secondary endpoints will be tested in the order in which they are listed in Section 8.3.2.

The analysis of the mean change from baseline at week 24 for 2-hour post-prandial glucose during a liquid meal test (2-h MTT) will be based on an ANCOVA model using LOCF methodology with terms for treatment group and baseline value in the model. Analyses of the mean change from baseline at week 24 for FPG, and total body weight will be performed using the same longitudinal repeated measures model as for the primary efficacy endpoint. The analysis of total body weight will compare the saxagliptin 5 mg plus dapagliflozin 10 mg add-on to metformin treatment group versus the saxagliptin 5 mg plus placebo added to metformin group only. Sensitivity analyses for FPG and total body weight will consist of ANCOVA analyses using LOCF methodology.

The proportion of subjects achieving a therapeutic glycemic response (defined as HbA1c < 7.0%) at Week 24 (LOCF) will be summarized by treatment group and compared between treatment groups using the methodology of Zhang, Tsiatis, and Davidian⁶ and Tsiatis, Davidian, Zhang, and Lu⁷ 95% confidence intervals for the response rate within each treatment group as well as for the difference in response rates between treatment groups will be calculated with adjustment for baseline HbA1c.

8.4.2.3 Other Efficacy Analyses

The percent of subjects who require glycemic rescue or discontinue study for lack of efficacy up to Week 24 will be assessed by summarizing the difference in percentages between treatment groups and by a time to event analysis using the Kaplan-Meier methodology.

Analyses of the mean change from baseline for continuous endpoints (AUC glucose, AUC insulin, AUC C-peptide and AUC glucagon obtained during a 2-h MTT) will be performed using the same longitudinal repeated measures model as for the primary efficacy endpoint. The percent change from baseline in lipids at Week 24 will be analyzed using a longitudinal repeated measures analysis of the logarithms of the post- to pre-treatment ratios with terms for treatment group, time, interaction of treatment and time, the natural logarithm (Ln) of the baseline measurement, and the interaction of Ln (baseline) and time the logarithms of the post-treatment to baseline ratios with terms for treatment group and the log of the baseline measurement as a covariate.

Values and changes from baseline at each scheduled time point for clinical laboratory parameters, body weight, and vital signs, including seated blood pressure and heart rate, will be summarized by treatment group using descriptive statistics.

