3.3.2.1 Randomization Criteria

Exclusion:

• FPG >270mg/dl as measured at Week -4

Note: At Week -4 a qualification check will be performed and subjects will be excluded, if their FPG is > 270 mg/dl. A re-test will be permitted within 7 days if the initial result was > 270 mg/dl but < 300mg/dl. Subjects will be excluded if the mean value of the Week -4 result and the re-test result is > 270 mg/dl.

Eligibility criteria for this study have been carefully considered to ensure the safety of the study subjects and to ensure that the results of the study can be used. It is imperative that subjects fully meet all eligibility criteria.

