3.5.1.1 Initiation of Rescue Medication

Pre-specified glycemic criteria (see Table 3.5.1.1), based upon central laboratory FPG and repeat, confirmatory FPG, have been established during the double-blind treatment period, starting at Week 6, and up to Week 24 visits, to determine eligibility for open label rescue medication.

Table 3.5.1.1:	Lack of Glycemic Control Criteria for Initiation of Rescue Medication		
Visit Label		Central Laboratory FPG	
Week 6		FPG > 270 mg/dL (15.0 mmol/L)	
After Week 6 to Week 12 (excluding Week 12)FPG > 240 mg/dL (13.3 mmol/L)		FPG > 240 mg/dL (13.3 mmol/L)	
Week 12 to Week 24 FPG > 200 mg/dL (11.1 mmol/L)		FPG > 200 mg/dL (11.1 mmol/L)	

Subjects with a central laboratory FPG value meeting the lack of glycemic control criterion at a pre-specified visit will be scheduled for a follow-up visit (within 3 - 5 days) to obtain a second central laboratory FPG value and review the subject's glucose meter readings. If the repeat central laboratory FPG value still meets the criterion, the subject must be rescued.

Subjects who meet rescue criteria in the double-blind treatment period must first complete the Rescue Visit procedures before receiving open-label rescue medication to ensure that important trial endpoint measurements are collected. (See Section 5.8.3.1) Following completion of the Rescue Visit, rescued subjects will be given open-label antidiabetic rescue medication (Insulin or other antidiabetic agents except GLP-1 analogs, other DPP4/SGLT2 inhibitors or metformin) to be initiated at the lowest starting dose and titrated in accordance with the approved product label in the applicable country at the discretion of the investigator, in addition to their double-blinded study medication. Rescued subjects will then continue in the double-blind treatment period according to their original visit schedule.

Note: Rescue medication will not be provided by Sponsor in this study.

Following initiation of open-label rescue antidiabetic medication, rescued subjects should be scheduled for titration visits to increase their antidiabetic medication dose, as tolerated and in accordance with the approved product label for that country and by their glycemic response and as per the Investigator's judgment.

3.5.2 Discontinuation Guidelines due to Protocol-Defined Major Hypoglycemia Episode or Recurrent Non-Major Hypoglycemia Episodes

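### The exploratory rescue comparison is planned without baseline adjustment, although rescue is triggered by FPG and baseline FPG is available; the comparison is valid but gives up some precision

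*Protocol*

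**What the plan says.** - Section 8.3.3 lists among the exploratory endpoints "The percent of subjects who require glycemic rescue or discontinue study treatment for lack of efficacy up to Week 24", and also the time to that event. Section 1.3 places the matching comparisons under the other objectives.
- Section 8.4.2.3 states that this percentage "will be assessed by summarizing the difference in percentages between treatment groups and by a time to event analysis using the Kaplan-Meier methodology". It names no covariate, test or model.
- Section 3.5.1.1 makes eligibility for rescue "based upon central laboratory FPG and repeat, confirmatory FPG". The thresholds are above 270 mg/dL at Week 6, above 240 mg/dL after Week 6 and before Week 12, and above 200 mg/dL from Week 12 to Week 24.
- Table 5.1 schedules FPG at Day 1. Section 8.4.1 lists "baseline HbA1c, baseline FPG, 2-hour post-prandial glucose during a liquid meal test" among the key baseline characteristics and defines baseline as the last measurement before the first double-blind dose.
- Section 8.4.2.2 treats the other binary glycemic endpoint differently: the confidence interval "for the difference in response rates between treatment groups will be calculated with adjustment for baseline HbA1c".
- Section 4.2 stratifies randomization by site only.

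**The concern.** An event defined by FPG crossing a threshold should be partly predictable from FPG at baseline. The protocol uses this principle for the HbA1c response, which it adjusts for baseline HbA1c. The repeated measures, ANCOVA and lipid models in Section 8.4.2 also carry a baseline term. The rescue endpoint is the exception, and no reason is given.

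What is at stake is the width of the interval around the rescue difference. Variation that baseline FPG could explain stays in the error. In any one trial, the part of the estimate that comes from a chance FPG difference between arms is not removed. A smaller matter is that Kaplan-Meier curves are estimated arm by arm, and Section 8.4.2.3 names no between-group measure for the time-to-event comparison.

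**Working it through.** **Inputs from the protocol.** Section 8.1 gives 172 randomized per arm: 163/(1 − 0.05) = 171.6, rounded up, and 3 × 172 = 516. Allocation is 1:1:1 (Section 4.2). The protocol gives no event rate, effect or power for the rescue endpoint, so there is no stated figure to reproduce.

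**Assumed inputs.** The event rate p0 in the reference arm is 5% to 30%, and p1 in the combination arm is 2% to 15%. Standardized baseline FPG, x, has correlation ρ of 0.3, 0.5 or 0.7 with a normal latent variable that produces the event when it passes a cut-off (a probit model).

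**Step 1: crude variance.** Var(crude) = [p0(1 − p0) + p1(1 − p1)]/172.

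**Step 2: variance with the best use of baseline FPG.** Let g0(x) and g1(x) be the event probabilities given x in the two arms. With equal arms,

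Var(adj) = [p0(1 − p0) − Var g0 + p1(1 − p1) − Var g1]/172 + Var(g1 − g0)/(2 × 172).

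**Worked case, 20% v 10%, ρ = 0.5.**
- Crude: (0.16 + 0.09)/172 = 0.001453, so SE = 0.0381.
- Numerical integration gives Var g0 = 0.0214, Var g1 = 0.0093 and Var(g1 − g0) = 0.0028.
- Adjusted: (0.1386 + 0.0807)/172 + 0.0028/344 = 0.001283, so SE = 0.0358.
- Reduction: 1 − 0.001283/0.001453 = 11.7%. The same precision without adjustment would need about 172 × (0.001453/0.001283 − 1) ≈ 23 more subjects per arm.

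**Reduction in variance over the assumed range.**

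| Rates (reference v combination) | Crude SE | ρ = 0.3 | ρ = 0.5 | ρ = 0.7 |
|---|---|---|---|---|
| 5% v 2% | 0.0198 | 1.8% | 6.2% | 16.7% |
| 10% v 5% | 0.0283 | 2.8% | 8.9% | 21.5% |
| 20% v 10% | 0.0381 | 3.9% | 11.7% | 25.8% |
| 30% v 15% | 0.0443 | 4.6% | 13.4% | 28.2% |

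The standard error itself falls by about 1% to 15%. For illustration, at 10% v 5% the power of a two-sided 0.05 test is 42% unadjusted and 43%, 46% or 51% adjusted.

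**Step 3: effect of a chance imbalance.** One standard error of the baseline FPG difference between arms is √(2/172) = 0.108 SD. The crude difference then moves by about ρ × [φ(z0) + φ(z1)]/2 × 0.108, where φ is the normal density at the cut-off for each arm. For 10% v 5% and ρ = 0.5 this is 0.5 × (0.1755 + 0.1031)/2 × 0.108 = 0.0075, or 0.75 percentage points. Over the table it runs from 0.25 to 2.2 points, which is 0.12 to 0.49 of the crude standard error.

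**Step 4: is the crude comparison valid?** In 3,000 simulated trials per setting, the mean crude difference was −0.049 to −0.050 for a true −0.05, and −0.099 to −0.101 for a true −0.10. With no true effect (10% in both arms), a Wald test at 0.05 rejected in 4.9%, 6.0% and 5.0% of trials for the three correlations, with Monte Carlo error about 0.4 points. A logistic model standardized over baseline FPG gave the same mean differences. Its standard deviation was 0.94 times the crude one at 20% v 10% and ρ = 0.5, in line with the 11.7% above.

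**The case against.** **The protocol is silent rather than opposed to adjustment.** It does not say unadjusted, and covariates for an exploratory endpoint are often left to the SAP, which is not at hand. This is fair, and the SAP may already add them. But Section 8.4.2.3 does state a method, and the same part of the protocol names a baseline term wherever it wants one. Read as written, the plan is a crude difference.

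**The endpoint is exploratory.** It lies outside the step-wise procedure and the sample size, while the HbA1c response is a ranked secondary endpoint, so a more careful analysis there is defensible. This stands and sets the severity.

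**Bias.** A reader might infer that a chance FPG imbalance biases the rescue result or inflates its type I error. The documents do not support that. Allocation is randomized, the crude difference is unbiased, and its standard error already includes such imbalance. The shift in Step 3 describes a single realised trial.

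**Size of the gain.** It cannot be derived from the protocol, and two features may hold it down. The composite includes discontinuation for lack of efficacy, for which no FPG criterion is given. Randomization also excludes "FPG >270mg/dl as measured at Week -4", which narrows the covariate. Both stand, so no single percentage should be quoted as the expected gain.

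**Adjustment has costs.** A Cox model gives a conditional hazard ratio, which differs from the marginal comparison, and it assumes proportional hazards. With few events in the combination arm, a covariate model can be unstable. This stands and is reflected in the fix.

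**Conclusion.** The point holds as a low-severity matter of efficiency. The planned rescue comparison is valid, but it leaves out an available baseline measurement of the variable that triggers rescue, while the comparable binary endpoint is adjusted. The loss is about 2% to 28% of the variance of the risk difference at 172 per arm. For reference-arm rates of 10% to 20% and a correlation of 0.3 to 0.5 it is about 3% to 12%. The event rates and the correlation are assumptions, and the model treats the whole composite as related to FPG. No primary or secondary conclusion is affected.

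**What to change.** In Section 8.4.2.3, or in the SAP before unblinding, specify that the difference in the percentage rescued or stopped for lack of efficacy is estimated with a 95% confidence interval by the covariate-adjusted method already cited in Section 8.4.2.2, with baseline FPG as covariate. Keep the crude percentages as a descriptive summary, and state in advance that the crude difference will be reported alone if events are too few for a stable fit.

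Optionally, add to the Kaplan-Meier curves one prespecified between-group comparison adjusted for baseline FPG. If a Cox model is used, say that its hazard ratio is conditional on baseline FPG and assumes proportional hazards, and treat it as a supplement.

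The cost is a few sentences and a little programming. No new data, visits or subjects are needed. The one small downside is possible instability if events are few in the combination arm.
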